2.4.5.2 Deaths

The following summaries of deaths will be generated for the all-treated population:

- Number (%) of patients who died by study period (on-treatment, post-treatment as defined in [Section 2.1.4.3](#)) and reasons for death by treatment received.
- Deaths in nonrandomized patients or randomized but not treated patients. A listing may be provided.

- Summary of AEs leading to death, by Primary SOC and PT
 - in context of disease progression (death within 30 days from last study treatment administration and for whom cause of death is disease progression),
 - in context other than PD (death within 30 days from last study treatment administration and for whom cause of death is different from disease progression, or death more than 30 days from last study treatment administration and for whom cause of death equals to adverse event)

Some listings might also be reported if judged more relevant.

2.4.5.3 Analyses of ocular examinations

Number (%) of visual symptoms will be provided.

During the treatment, change from baseline will be summarized.

For slit lamp examination, patients with abnormal or normal status will be provided. For patients with abnormal status, number of patients with corneal mycrocysts, corneal deposits, corneal erosion, corneal ulcer, and corneal inflammation at one of the eyes will be described. Number of patients with clinically significant findings will be reported with corresponding adverse event.

For Schirmer's test, descriptive statistics on the result will be provided. Patients will be classified into four classes with anesthetics: normal ≥ 15 mm, mild 14-9 mm; moderate 8-4 mm; severe < 4 mm and ocular adverse events for the classification severe at baseline will be reported.

For tonometry test, number (%) of patients with abnormal/normal status with and without dilation at baseline will be provided. During the treatment, descriptive statistics of the change from baseline without dilation for each eye will be provided.

2.4.5.4 Analyses of laboratory variables

Hematological and clinical biochemistry toxicities will be assessed from laboratory test parameters defined in [Section 2.1.4.4](#).

The frequency of patients in each grade of laboratory test during treatment will be summarized. For patients with multiple occurrences of the same laboratory variable during the treatment, the maximum grade (worst) per patient will be used.

The denominator used for percentage calculation is the number of patients with at least 1 evaluation of the laboratory test during the considered observation period.

The summary table will present the frequency of patients with any grade of abnormal laboratory tests and with Grade 3-4 abnormal laboratory tests.

For the non-NCI gradable parameters (monocytes, eosinophils, basophils, chloride, total protein, BUN, LDH, urea, direct bilirubin), frequency of evaluable patients outside normal ranges will be provided.

Regarding calculated creatinine clearance, a summary of the lowest value recorded by patient will be provided using summary statistics. Frequencies by class (≥ 90 mL/min, ≥ 60 mL/min and < 90 mL/min, ≥ 30 mL/min and < 60 mL/min, ≥ 15 mL/min and < 30 mL/min, < 15 mL/min) will also be provided.

Moreover, a listing of possible Hy's law cases identified (eg, patients with any elevated AST or ALT of > 3 ULN **and** elevated Total bilirubin > 2 ULN, 1 day apart), will be provided, displaying ALT, AST, Total bilirubin and ALP values.

A summary reporting the number of patients with at least one positive serum pregnancy test during the study will be provided.

2.4.5.5 Analyses of vital sign variables

Vital signs parameters are described in [Section 2.1.4.5](#).

- A summary of baseline results will be provided for all parameters.
- For ECOG performance status, a shift table will be provided for the last and worst evaluations respectively relative to baseline.
- For blood pressure (SBP, DBP), a table will be provided with the last and worst evaluations (minimum and maximum value). In addition, for blood pressure, a graph describing mean changes from baseline and associated +/- SEM will also be done throughout the on-treatment period.
- Weight and BSA will be summarized at baseline only

For blood pressure parameters and weight, potentially clinically significant abnormality (PCSA) values are defined as abnormal values considered medically important by the Sponsor according to predefined criteria/thresholds based on literature review ([Appendix E](#)).

Moreover, the incidence of PCSAs at any time during the treatment-emergent adverse event period will be summarized irrespective of the baseline level and/or according to the following baseline status categories:

- Normal/missing
- Abnormal according to PCSA criterion or criteria

2.4.5.6 Analyses of electrocardiogram variables

The incidence of patients with at least 1 abnormal ECG at end of treatment will be summarized or according to the following baseline status categories:

- Normal/missing
- Abnormal

2.4.6 Analyses of biomarkers

Parameters described in [Section 2.1.7](#) will be summarized on the all treated population using descriptive statistics.

2.4.6.1 Descriptive analyses

CA6 expression

At the end of part 1, baseline CA6 expression in tumor tissue will be summarized as the percent of positive cells at intensity 3+ and $\geq 2+$ on the sum of membrane, as well as with the H-score on the sum of membrane. At the end of part 2, percent of positive cells at intensity 1+ will also be described. Descriptive analyses of cytoplasmic data may also be considered.

Baseline circulating CA6 will also be summarized:

- The relation between circulating CA6 at baseline and the percentage of positive cells of CA6 expression at intensity ≥ 2 in tumor tissue sample at baseline by IHC will be explored on the overall membrane by a scatter plot. Responders and non-responders will be identified by different symbols or colors.
- A monotonic correlation evaluated with Spearman's rank-order correlation coefficient could be done between the circulating CA6 at baseline and the percent of positive cells at intensity $\geq 2+$ of CA6 expression by IHC.

Genetic alterations

For each genetic alteration listed in [Section 2.1.7.3](#), a shift table will be performed between baseline and end-of-treatment (EOT) status to detect mutation changes.

2.4.6.2 Analyses between biomarkers expression and efficacy endpoints

CA6 expression

The analyses between CA6 IHC expression and efficacy endpoints will include the two expression cohorts (Part 2a and Part 2b).

To assess the potential link between CA6 IHC expression and efficacy endpoints, CA6 IHC expression will be described according to patients' status (responder/non responder).

Following graphical representations will be provided:

- Boxplots of percent of positive cells of CA6 at intensity $\geq 2+$ according to patients' status (responder/non-responder)
- Potential link between percent of positive cells CA6 expression at intensity $\geq 2+$ and the best relative tumor shrinkage will be assessed graphically with a Waterfall chart.
- Scatter plot of percent positive cells of CA6 in intensity $\geq 2+$ by the best relative tumor shrinkage

To detect an association between biomarker status and ORR, a 1-sided Fisher's exact test will be calculated considering the number of responses in each cohort (overexpression cohort and mild expression cohort) and the sample size of the cohorts.

Genetic alterations

To assess the potential link between genetic alterations and efficacy data, the following analyses will be summarized for each genetic alteration:

- Number and percentage of patients with each genetic alteration status (baseline and EOT) by response status (responder/non-responder).
- For each genetic alteration, a waterfall plot of the best relative tumor shrinkage according to genetic alteration status will be displayed.

These analyses will be performed on the all-treated population.

2.4.7 Analyses of pharmacokinetic variables

PK parameters of SAR566658, naked huDS6 (SAR404461) and unconjugated maytansinoids (DM4 and Me-DM4) will be summarized with descriptive statistics (arithmetic and geometric means, standard deviation, coefficient of variation, minimum, median, and maximum).

The relationship between PK parameters and safety/efficacy endpoints may be investigated using logistic regression models with covariates selection using stepwise procedure.

Those estimates will then be investigated as prognostic factors for clinical outcome including safety and efficacy endpoints, if possible.

Previous PK data collected in other clinical studies such as TED10499, in which intensive blood sampling protocols were used, may be considered to help in model building.

2.4.8 Analyses of immunogenicity variables

Number (%) of patients with pre-existing ATAs, number (%) of ATAs negative patients, number (%) of inconclusive patients, number (%) of ATAs positive patients, number (%) of patients with treatment boosted ATAs, number (%) of patients with treatment induced ATAs (either transient or persistent) will be carried out.

Prevalence and incidence will be presented as well as descriptive statistics of titers and a listing of ATAs time point assessment.

The impact of positive immune response may be evaluated on efficacy, PK and safety endpoints.

2.4.9 Further therapy after discontinuation of investigational medicinal product administration during the study

Number (%) of patients with at least one post-treatment anti-cancer therapy (post-treatment systemic anti-cancer treatment, post-treatment radiotherapy or post-treatment surgery combined) will be summarized.

Moreover, a summary table will be provided for post-treatment anti-cancer therapy based on WHO-DD coding. Descriptive statistics will be also provided for post-treatment radiotherapy and post-treatment surgery.

2.5 DATA HANDLING CONVENTIONS

2.5.1 General conventions

The following formulas will be used for computation of parameters.

Demographic formulas

Body surface area value will be derived using the variation of DuBois and DuBois formula:

$$\text{BSA (m}^2\text{)} = \text{weight in kg}^{0.425} \times \text{height in cm}^{0.725} \times 0.007184$$

Renal function formulas

Creatinine clearance value will be from the equation of Cockcroft and Gault:

$$\text{Creatinine clearance} = \frac{(140 - \text{age [years]} \times \text{body mass [kg]})}{\text{Plasma creatinine (mg/dL)} \times 72} \times \text{Gender correction factor (male: 1.00; female: 0.85)}$$

Creatinine clearance in ml/min at a cycle will be calculated using last weight assessed before or at the date of serum creatinine measurement.

Corrected calcium formula

$$\text{Corrected Calcium} = \text{Serum Calcium (in mmol/L)} + 0.8 (4 - \text{serum albumin [in G/dL]})$$

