- e **Physical examination** will include: examination of major body systems, height (at baseline only), body weight, ECOG PS, and vital signs (temperature, blood pressure). At the follow-up visit, only ECOG PS and weight will be collected. Signs and symptoms will be reported in the eCRF as AEs only if they are still present at the time of first IMP administration.
- f **Hematology:** hemoglobin, WBC with differential, platelet counts. These tests will be done weekly for Cycles 1 and 2. If Grade 4 neutropenia occurs, assess ANC every 2-3 days until ANC $\geq 0.5 \times 10^9/L$.
- g **Coagulation:** INR.
- h **Blood chemistry:** liver function tests: AST, ALT, total bilirubin, conjugated bilirubin, AP, electrolytes: sodium, potassium, calcium, phosphate, and chloride. Renal function tests: creatinine and BUN or urea. Others: glucose, LDH, albumin, and total proteins. These tests will be done weekly during the 2 first cycles then every 3 weeks for subsequent cycles, except for BUN and chloride that will be done weekly only during the first cycle. Additional tests will be performed when clinically appropriate. In case of Grade ≥ 3 liver function abnormal tests, additional tests will be done every 2 to 3 days until recovery to baseline value.
- i **Serum pregnancy test:** women of child-bearing potential must have a negative serum pregnancy test result within 7 days prior to the initial dose of IMP and at the end of treatment evaluation (between D22 and D30 after the last IMP administration). The serum pregnancy test will also be performed before each cycle, only in countries where it is a regulatory requirement.
- j **12-lead ECG** is required at baseline and at end of treatment. To be repeated as clinically indicated.

- k* **SAR566658 administration:** on Day 1 and Day 8 of each treatment cycle, the patient's BSA will be determined using the current weight and baseline height. For patients with a BSA >2.0 m², the dose will be calculated on the basis of 2.0 m² BSA. Premedication with histamine H1 antagonist is required: diphenhydramine 50 mg given orally approximately 1 hour before SAR566658 administration.

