7.2.2 Exclusion criteria related to the current knowledge of Sanofi compound

- E 14. Acquired immunodeficiency syndrome (AIDS-related illnesses) or known HIV disease requiring antiretroviral treatment.
- E 15. Known active hepatitis A, B, or C infection that requires treatment.
- E 16. Known intolerance to infused protein products including other monoclonal antibodies and ADCs.
- E 17. Poor bone marrow reserve as defined by absolute neutrophil count (ANC) $<1.5 \times 10^9/L$ or platelets $<100 \times 10^9/L$ or hemoglobin $<9 \text{ g/dL}$.
- E 18. Poor organ function as defined by 1 of the following:
 - a) Total bilirubin $>1.5 \times$ upper limit of normal (ULN) (except patients with Gilbert's syndrome: total bilirubin $\leq 3.0 \times$ ULN, with direct bilirubin $\leq 1.5 \times$ ULN),
 - b) Aspartate aminotransferase (AST), alanine aminotransferase (ALT), or alkaline phosphatase $>2.5 \times$ ULN; except $>5 \times$ ULN in case of documented liver metastasis or alkaline phosphatase $>5 \times$ ULN in case of documented bone metastasis,
 - c) Serum creatinine $>1.5 \times$ ULN, except if calculated creatinine clearance $\geq 60 \text{ mL/min}$ (as per Cockcroft-Gault formula; see [Appendix E](#)).
- E 19. Symptomatic peripheral neuropathy Grade ≥ 2 (NCI CTCAE v.4.03).
- E 20. Previous history of chronic corneal diseases (even if asymptomatic) or unresolved acute nonrecurrent corneal conditions.
- E 21. Patients wearing contact lenses who are not willing to stop wearing them for the duration of the study.
- E 22. Medical conditions requiring concomitant administration of strong CYP3A4 inhibitors, unless it can be discontinued at least 2 weeks before 1st administration of SAR566658 (see [Appendix F](#)).
- E 23. Contraindications to the use of ophthalmic vasoconstrictor and/or corticosteroid as per package insert of each drug, including the following: increased intraocular pressure, prior or current glaucoma, narrow-angle glaucoma, ongoing eye infection, uncontrolled hypertension, known/suspected allergy to constituents of the preparation (such as sodium bisulfite).

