11.4.5.5 Analyses of laboratory safety variables

Clinical laboratory values will be analyzed after conversion into standard international units. Clinical laboratory parameters will be graded according to the NCI CTCAE v4.03 scale, when applicable, and analyzed according to the out-of-normal laboratory range value, when the NCI CTCAE scale is not applicable.

The number of patients with abnormal laboratory tests at baseline (Grade ≥ 1) will be presented by grade. The frequency of patients in each grade of laboratory test during treatment will be summarized. For patients with multiple occurrences of the same laboratory variable during the on-treatment period, the maximum grade (worst) per patient will be used. The denominator used for the percentage calculation is the number of patients with at least 1 evaluation of the laboratory test during the considered observation period.

When the NCI CTCAE v4.03 scale is not applicable, the number of patients with a treatment-emergent out-of-normal laboratory range value will be displayed.

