2.1.4.4 Laboratory safety variables

Laboratory data consists of blood analysis, including hematology and biochemistry.

Blood samples for clinical laboratories will be taken at Day 8, Day 15 and Day 21 during the first two cycles (except for INR only at Day 21) and then at Day 8 and Day 21 for hematology and Day 21 for clinical chemistry and INR at subsequent cycles and then at end of treatment. The laboratory parameters will be classified as follows:

- Hematology:
 - **Red blood cells (RBC) and platelets and coagulation:** hemoglobin, platelet count, international normalized ratio (INR).
 - **White blood cells (WBC):** WBC with differential (neutrophils, lymphocytes, monocytes, basophils, eosinophils), absolute neutrophil count (ANC).

- Clinical chemistry:
 - **Metabolism:** blood glucose, lactate Dehydrogenase (LDH), total protein, albumin,
 - **Electrolytes:** sodium, potassium, chloride, calcium, corrected serum calcium (calculated according to Corrected calcium formula, see [Section 2.5.1](#)), phosphate,
 - **Renal function:** serum creatinine, creatinine clearance (calculated according to both Cockcroft-Gault formula, see [Section 2.5.1](#)), urea or blood urea nitrogen (BUN),
 - **Liver function:** alanine aminotransferase (ALT), aspartate aminotransferase (AST), alkaline phosphatase, total and direct bilirubin.

Moreover, serum pregnancy test will be performed at baseline, during on-treatment period and end of treatment period for women of child bearing potential.

Laboratory values will be analyzed after conversion into standard international units by data management. These converted values will be graded according to the NCI-CTCAE version 4.03 whenever applicable, using laboratory normal ranges (liver function tests, creatinine, creatinine clearance, LDH) provided by the laboratory analyzing the sample whenever possible or using generic normal ranges for other parameters (see Appendix G). When the NCI-CTCAE is not applicable, laboratory values “out of normal ranges” will be summarized.

For each laboratory parameter, each assessment performed from the 2nd day of cycle N to the 1st day of cycle N+1 will be assigned to cycle N. The 1st day of any cycle will be the date of the 1st study treatment infusion for this cycle.

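### The SAP's corrected-calcium formula applies a coefficient of 0.8 to calcium in mmol/L; if 0.8 belongs to calcium in mg/dL, the albumin correction is about four times too large

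*SAP*

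**What the plan says.** SAP 2.5.1 (General conventions) sets out the formulas to be used for computing derived parameters. For corrected calcium it prints "Serum Calcium (in mmol/L)} + 0.8 (4", from which it subtracts "serum albumin [in G/dL" inside the bracket. Both units are named: calcium in mmol/L and albumin in g/dL, with 4 as the albumin reference. No unit, source or conversion step is given for 0.8.

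The formula is put to use in SAP 2.1.4.4, which lists among the electrolytes "sodium, potassium, chloride, calcium, corrected serum calcium (calculated according to Corrected calcium formula". The same section states "Laboratory values will be analyzed after conversion into standard international units by data management", so calcium will be in mmol/L when the formula is applied. Neither document, as supplied, contains another corrected-calcium formula.

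On grading, protocol 11.4.5.5 says "Clinical laboratory parameters will be graded according to the NCI CTCAE v4.03 scale, when applicable". SAP 2.4.5.4 lists the parameters that cannot be graded, and calcium is not among them.

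**The concern.** The albumin term is added directly to a value in mmol/L, so 0.8 has to mean 0.8 mmol/L of calcium per g/dL of albumin. That is a very large correction. It looks like a coefficient meant for calcium in mg/dL that has been attached to an SI label.

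The protocol's chemistry panel (section 1.3, blood chemistry footnote) measures calcium and albumin but not corrected calcium: "Others: glucose, LDH, albumin, and total proteins. These tests will be done weekly during the 2 first cycles then every 3 weeks" for later cycles. Every corrected value would therefore come from this formula. The organ-function exclusion in protocol 7.2.2 ("Poor organ function as defined by 1 of the following") sets no albumin limit, so patients with albumin away from 4 g/dL are not screened out.

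At stake is the reliability of one derived safety variable. Low albumin would produce falsely high corrected calcium and high albumin falsely low. If the corrected value is the one graded, the calcium rows of the laboratory toxicity tables would be wrong in the same directions.

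**Working it through.** The documents give no worked corrected-calcium value, so there is no stated figure to reproduce. The check is a unit conversion.

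**Inputs from the SAP (2.5.1):** calcium in mmol/L, coefficient 0.8, albumin in g/dL, albumin reference 4.

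**Inputs from outside the documents:**
- Molar mass of calcium 40.078 g/mol (physical constant), so 1 mmol/L = 4.008 mg/dL.
- Assumption: 0.8 is the coefficient for calcium in mg/dL per g/dL of albumin. A range of 0.6 to 1.0 is shown below.
- Illustrative measured calcium of 2.20 mmol/L. The documents give no calcium or albumin distribution.

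**Step 1, the consistent coefficient.** 0.8 / 4.008 = 0.1996, about 0.2 mmol/L per g/dL. The printed coefficient divided by this is 0.8 / 0.1996 = 4.01. The error per g/dL of albumin away from 4 is 0.8 − 0.2 = 0.6 mmol/L. Put the other way, the printed term equals 0.8 × 4.008 = 3.21 mg/dL per g/dL.

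**Step 2, size at calcium 2.20 mmol/L.** Printed value = 2.20 + 0.8 × (4 − albumin); consistent value = 2.20 + 0.1996 × (4 − albumin).

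| Albumin (g/dL) | Printed (mmol/L) | Consistent (mmol/L) | Difference |
|---|---|---|---|
| 2.5 | 3.40 | 2.50 | +0.90 |
| 3.0 | 3.00 | 2.40 | +0.60 |
| 3.5 | 2.60 | 2.30 | +0.30 |
| 4.0 | 2.20 | 2.20 | 0 |
| 4.5 | 1.80 | 2.10 | −0.30 |

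Cross-check at albumin 3.0, working in mg/dL: 2.20 × 4.008 = 8.82; 8.82 + 0.8 = 9.62; 9.62 / 4.008 = 2.40 mmol/L.

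**Step 3, sensitivity to the assumed coefficient.**

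| mg/dL coefficient | In mmol/L | Printed correction too large by | Error per g/dL (mmol/L) | Consistent value at calcium 2.20, albumin 3.0 |
|---|---|---|---|---|
| 0.6 | 0.150 | 5.3 times | 0.65 | 2.35 |
| 0.8 | 0.200 | 4.0 times | 0.60 | 2.40 |
| 1.0 | 0.250 | 3.2 times | 0.55 | 2.45 |

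The printed formula gives 3.00 in every row.

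**Step 4, a plausibility check that does not use the mg/dL assumption.** At 0.8 mmol/L per g/dL, 4 g/dL of albumin accounts for 0.8 × 4 = 3.2 mmol/L of calcium. If total serum calcium is 2.20 to 2.60 mmol/L (assumed), that is more than all the calcium present. Equivalently, for a corrected value in that range, the formula has measured calcium reach zero at an albumin between 4 − 2.60/0.8 = 0.75 and 4 − 2.20/0.8 = 1.25 g/dL. With 0.2, 4 g/dL of albumin accounts for 0.8 mmol/L and measured calcium stays positive at every albumin value.

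**The case against.** The strongest objection is that the premise lies outside the documents. Neither says which calcium unit 0.8 belongs to, and the 0.6 to 1.0 range is also an assumption. The plausibility check does not escape this entirely: it needs an assumed normal calcium range and extends a straight line to albumin values that few patients would have. This stands as a limit on the proof. It does not rescue the formula, because the printed correction is at least three times too large across the whole range, and the plausibility check points the same way by a separate route.

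A second objection is that 0.2 is not the only repair. Keeping 0.8, computing in mg/dL and then converting would do equally well. That is correct, but the line must change either way, since SAP 2.1.4.4 requires SI units.

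A third is that the consequence is small and partly conditional. SAP 2.4.5.4 reaches corrected calcium only through its general reference to 2.1.4.4. Neither document says whether corrected or uncorrected calcium is graded; if uncorrected, no grade changes. No shift in grades can be counted without an albumin distribution, and the absence of an albumin exclusion does not show that low values will be common. Calcium does not appear in the eligibility criteria or in the protocol's dose-modification table, and the predefined safety criteria rest on related adverse events. All of this stands, and it is why the point is rated minor.

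**Conclusion.** The formula is wrong as written. On the assumption that 0.8 is the mg/dL coefficient, the albumin correction is about four times too large, an error of about 0.6 mmol/L per g/dL of albumin away from 4. The direction and rough size hold for assumed coefficients from 0.6 to 1.0. The error applies to the correction term, not to the whole calcium value, and vanishes at albumin 4.0 g/dL.

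Severity is minor. The effect is confined to corrected serum calcium and any grade derived from it. The objective response rate, the interim and final response boundaries (2 of 14, 6 of 14 and 7 of 29) and the Bayesian monitoring of predefined safety criteria are untouched. Nothing is claimed about the albumin unit, which the formula names, or about the generic ranges in SAP Appendix G, which are not in the supplied text.

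**What to change.** In SAP 2.5.1, replace the line with: corrected calcium (mmol/L) = calcium (mmol/L) + 0.2 × (4 − albumin in g/dL). If the SI database holds albumin in g/L, the equivalent is + 0.02 × (40 − albumin in g/L), since 1 g/dL = 10 g/L. Cite the source of the coefficient beside the formula. It would also help to say in SAP 2.4.5.4 whether corrected or uncorrected calcium is graded.

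The correction is one line in the SAP, best made before programming. It needs no protocol change and no additional data.
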